9.5. Unscheduled Visits

Unscheduled visits are allowed for the following reasons:

- Management of an adverse event or serious adverse event;
- Dose de-escalation;
- Any time the investigator feels that it is clinically appropriate for subject safety.

At a minimum, unscheduled visits should include collection of adverse events and vital signs. Additional conversations may be necessary with the medical monitor following an unscheduled visit to assess subject safety.

9.6. Pregnancy

9.6.1. Women of Childbearing Potential

Women will be asked to self-report their pregnancy status at screening. We are relying on self-reporting of pregnancy because we do not want to delay the preventive treatment for COVID-19 to those who are working in a high-risk environment. The study investigators believe that the risk of contracting COVID-19 may be worse than taking hydroxychloroquine.

Women of childbearing potential (WOCBP) are those who are not surgically sterile (no history of bilateral tubal ligation, hysterectomy, or bilateral salpingo-oophorectomy) do not have fallopian inserts with confirmed blockage, have not had reproductive potential terminated by radiation, and are not postmenopausal for at least 1 year.

9.6.2. Methods of Birth Control

During Screening, while taking study drug and until 30 days following administration of the final dose of study medication, WOCBP must practice one of the following acceptable methods of birth control:

- Use double barrier contraception method defined as male use of a condom and female use of a barrier method (*e.g.*, contraceptive sponge, spermicidal jelly or cream, diaphragm [always use with spermicidal jelly/cream]);

- Use of hormonal contraceptives (oral, parenteral, vaginal, or transdermal) for at least 90 days prior to start of study drug administration;
- Use of an intrauterine device;
- monogamous partner with a vasectomy;
- Abstain from sexual intercourse completely. Complete abstinence from sexual intercourse is only acceptable if it is the preferred and usual lifestyle of the individual. Periodic abstinence is not permitted.

During Screening, while taking study drug and until 30 days after the final dose of study medication is taken, males who have female partners of childbearing potential must practice one of the following methods of birth control:

- Have had a vasectomy (at least 6 months earlier);
- Use double barrier contraception method, defined as male use of a condom and female use of a barrier method (*e.g.*, contraceptive sponge, spermicidal jelly or cream, diaphragm [always use with spermicidal jelly/cream]);
- Partner use of an intrauterine device;
- Partner use of hormonal contraceptives (oral, parenteral, vaginal or transdermal) for at least 90 days prior to start of study drug administration;
- Abstain from sexual intercourse completely. Complete abstinence from sexual intercourse is only acceptable if it is the preferred and usual lifestyle of the individual. Periodic abstinence is not permitted.

9.7. Serious Toxicities

In the case of serious toxicities, the investigator may choose to interrupt treatment with hydroxychloroquine. Dose reductions are permitted to manage tolerability issues. Once a subject's dose has been reduced, that dose should be maintained until the Day 49 visit. Subjects who resume therapy after an interruption will follow the originally planned study schedule.

9.8. Study Procedures

The following sections describe each assessment. The timing of these assessments is noted in [Table 3](#). All Day 1 procedures, except AE assessments, should be completed prior to administration of first dose of study drug.

9.8.1. Informed Consent

Written informed consent (see [Section 15.3](#)) must be obtained from the subject before any study-related procedures are performed, and again if there is a change in the study procedures that would affect the subject's willingness to participate.

9.8.2. Informed Consent For Optional Viral Serology Sub-Study

Individuals who are willing to participate in the viral serology sub-study, which is optional, will sign a separate consent form prior to the collection of samples.

9.8.3. Inclusion/Exclusion

Inclusion and exclusion criteria must be reviewed as indicated in [Table 3](#). Subjects must meet all of the inclusion and none of the exclusion criteria for entry in the study. Investigators should contact the medical monitor with any questions regarding eligibility prior to enrolling the subjects on Day 1.

9.8.4. Demographics and Baseline Disease Characteristics

Demographic data including sex, age, race, and ethnicity, will be collected as indicated in [Table 3](#). Baseline disease characteristics will be collected as indicated in [Table 3](#).

9.8.5. Prior and Current Concomitant Medications

The name, dose, and frequency must be recorded for all medications that the subject is taking. All allowed and excluded medications should be recorded including all prescription drugs, herbal products, vitamins, minerals, and over-the-counter medications. Trade or generic drug names should be used where possible. Concomitant medications will be reviewed as indicated in [Table 3](#) and all changes will be recorded.

9.8.6. Current Background Medications

The name, dose, and frequency must be recorded for all background medications that the subject is taking. Trade or generic drug names should be used where possible. Additional background PAH medications may only be prescribed after a clinical worsening event is confirmed.

9.8.7. Medical History

A complete medical history (*e.g.*, per subject report) that includes all medical history within the past 5 years must be collected. Medical history will be recorded as indicated in [Table 3](#).

9.8.8. Height

Height will be self-reported as indicated in [Table 3](#).

9.8.9. Weight

Weight will be self-reported as indicated in [Table 3](#).

9.8.10. Body Temperature Measurements

Body temperature will be measured as indicated in [Table 3](#).

9.8.11. Cough Visual Analog Scale

Cough visual analogue scale (VAS, 0–100 mm) will be recorded as indicated in [Table 3](#) to assess cough severity in patients with chronic cough. Please refer to appendix II for cough visual analogue scale template.

9.8.12. Exposure Assessment

Subjects will be questioned about potential exposure to COVID-19 infection over the past 7 days as indicated in [Table 3](#) to quantify ongoing risk of infection. Please refer to Appendix III for more details on exposure assessment questionnaire.

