Based on more than 500 genetic sequences submitted to GISAID (the Global Initiative on Sharing All Influenza Data), the virus has not drifted to significant strain difference and changes in sequence are minimal. There is no evidence to link sequence information with transmissibility or virulence of severe acute respiratory syndrome coronavirus 2 (SARS-CoV-2), the virus that causes COVID-19.

SARS-CoV-2, like other emerging high-threat pathogens, has infected health-care workers in China and several other countries. To date, however, in China, where infection prevention and control was taken seriously, nosocomial transmission has not been a major amplifier of transmission in this epidemic. Epidemiological records in China suggest that up to 85% of human-to-human transmission has occurred in family clusters and that 2055 health-care workers have become infected, demonstrating that patient to healthcare worker is tractable. However, there have been no major nosocomial outbreaks and some supporting evidence that some health-care workers may have acquired infection or transmitted the infection to their families. These findings suggest that close and unprotected exposure is required for transmission by direct contact or by contact with fomites in the immediate environment of those with infection. Continuing reports from outside China suggest the same means of transmission to close contacts

and persons who attended the same social events or were in circumscribed areas such as office spaces or cruise ships. It has been suggested that a healthcare worker that had 15-30 min of exposure within 6 feet of an infected patient without PEP could acquire the infection.

Intensified case finding and contact tracing are considered crucial by most countries and are being undertaken to attempt to locate cases and to stop onward transmission. Confirmation of infection at present consists of PCR for acute infection, and although many serological tests to identify convalescent antibodies which confer potential immunity are being developed they require validation with well characterized sera before they are reliable for general use.

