7. INVESTIGATIONAL PLAN

7.1. Overall Study Design

This prospective open label trial will study the safety, tolerability, and efficacy of hydroxychloroquine in qualified health care workers.

Qualified individuals will be administered hydroxychloroquine twice a day on day 1 (two 200 mg twice a day) and once a week (two 200 mg) afterwards for a total of 7 weeks. Dose de-escalation is permitted during the study if indicated clinically. Please refer to [Section 7.3.1](#) for additional details on dose de-escalation.

All study individuals will follow the same visit and assessment schedule. Following study enrollment, participants will be scheduled to be assessed in person at Days 7, 14, 21, 28, 35, 42 and 49.

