7.5. Schedule of Assessments

[Table 3](#) lists the overall schedule of assessments for the study.

Table 3: Schedule of Assessments

Assessment	Study Day (Day)	Screen A ^a	Day 1 ^b	Day 7 Day 7±3	Day 14 Day 14±3	Day 21 Day 21±3	Day 28 Day 28±3	Day 35 Day 35±3	Day 42 Day 42±3	Day 49 ^j Day 49±3 (End of study visit)
Informed consent		X								
Inclusion/ exclusion		X	X ^c							
Self-reported Pregnancy Status ^d		X	X	X	X	X	X	X	X	X
Demographics and baseline disease characteristics		X								
Prior and Concomitant medications		X	X	X	X	X	X	X	X	X
Current background medications		X	X	X	X	X	X	X	X	X
Medical history		X								
Self-reported Height		X								
Self-reported Weight		X								
Body temperature		X	X	X	X	X	X	X	X	X
Study drug administration			X	X	X	X	X	X	X	
Dispense study drug ^e			X	X	X	X	X	X	X	
Collect study drug ^f				X	X	X	X	X	X	X
nasopharyngeal (NP) sampling			X	X	X	X	X	X	X	X
Adverse event collection			X ^g	X	X	X	X	X	X	X
Visual analogue scale (VAS) for cough severity		X	X	X	X	X	X	X	X	X
Exposure assessment		X	X	X	X	X	X	X	X	X
Virus serology ^h		X			X		X		X ⁱ	

^a Total Screening period should not exceed 30 days. Screening and Day 1 can be completed in the same visit.

^b Day 1 is the day of administration of the first dose. **On Day 1, all procedures should be performed before study drug administration.**

^c Screening eligibility procedures do not need to be repeated on Day 1; however, a review of any changes in eligibility criteria should be evaluated prior to Day 1 procedures

^d Female participants will be asked with respect to their pregnancy as a verbal check

^e Depending on the availability of the drug supply, the schedule of drug dispensing might change

^f If the schedule for drug dispensing changes, the arrangements for drug collection will change accordingly

^g AE assessments on Day 1 should be performed following study drug administration

^h Only applicable to those who choose to participate in the optional viral serology study

ⁱ Individuals who terminate from the study prior to the Day 49 study visit should return to the clinic as soon as possible for early termination assessments (*i.e.*, Day 49 Day Prior and end-of-treatment visits). Participants should complete the end-of-treatment procedures, including assessments, prior to any adjustments being made to their treatment regimen.

^j If final serology draw not collected at Day 42, it can be collected at day 49

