18.2 Appendix II: Cough Visual Analog Scale

18.3 Appendix III: Exposure Assessment Questionnaire

Exposure Questions		Visit:		Date		
#	Question	Details			Comments	
1	Number of shifts worked in the last 7d (in ICU/ED, +other COVID-19 unit)		Number of hours worked in last 7 d? (in ICU/ED, +COVID unit)			
2	Were you present in the room for a procedure likely to generate higher concentrations of respiratory secretions or aerosols ¹ ?	 no  yes	If yes:	List details (procedures, frequency, duration, etc.)		
3	Did you have extensive body contact with a +COVID-19 pt (e.g. rolling the patient, assisting in ADLs)?	 no  yes	If yes:	List details (activity, frequency, duration, etc.)		
4	Did you have prolonged close contact with a suspected/confirmed +COVID-19 pt (within 6 feet for > 15 min cumulatively in 1 or more shifts)?	 no  yes	If yes:	Were you in contact with secretions and/or excretions?	 no  yes	If Yes, did secretions contact unprotected:  Mouth  Eyes  Nose  hands

¹Examples: CPR, manual respiration, intubation, extubation, bronchoscopy, nebulizer therapy, or sputum induction

Staff initials: _____

Exposure Questions -continued			Visit:	Date
#	Question	Details	Comments	
5	Do you feel your PPE has been adequate?	 no  yes	If no:	Please describe:
6	Did you have unprotected exposures not described above (eg incomplete PPE for any duration with COVID19 patient):			

Staff initials: _____

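### The exposure form does not prompt for household or community contact, and its fixed 7-day look-back can leave days unasked when visits drift

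*Protocol*

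**What the plan says.** Protocol Section 9.8.12 sets a look-back of one week: "Subjects will be questioned about potential exposure to COVID-19 infection over the past 7 days". It gives the purpose as "to quantify ongoing risk of infection". Table 3 schedules the assessment at Screening, Day 1 and every visit through Day 49. Under Section 7.1, "participants will be scheduled to be assessed in person at Days 7, 14, 21, 28, 35, 42 and 49", and Table 3 gives each of those visits a ±3-day window. On the run-in, Table 3 notes: "Total Screening period should not exceed 30 days. Screening and Day 1 can be completed in the same visit".

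The form is in Appendix III. Item 1 asks for "Number of shifts worked in the last 7d (in ICU/ED, +other COVID-19 unit") and the matching hours; it is the only item with the 7-day period printed on it. Item 2 asks about aerosol-generating procedures. Item 3 asks "Did you have extensive body contact with a +COVID-19 pt (e.g. rolling the patient, assisting in ADLs"), and item 4 asks about prolonged close contact with a patient, defined as "within 6 feet for > 15 min cumulatively in 1 or more shifts". Item 5 asks whether PPE was adequate. Item 6 is an open question on other unprotected exposures; its one example is incomplete PPE with a patient. No item mentions household, family or community contact.

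The Introduction reports, from records in China, that "up to 85% of human-to-human transmission has occurred in family clusters". Section 7.3 lets participants choose their arm. Protocol Section 12.2.1 and SAP Section 6.1 plan a mixed model that controls for confounders, none of which is named.

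**The concern.** With self-chosen arms, nothing in the design balances infection risk between those who take hydroxychloroquine and those who join the registry. Any separation of drug effect from difference in risk must come from measured covariates. The exposure form is the only repeated measure of infection risk in the protocol, so what it fails to ask cannot be adjusted for later.

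Two features limit it. First, exposure outside work is not prompted. A participant living with an infected relative, with few shifts and good PPE, could be recorded as low exposure. Second, the recall period is fixed while the interval between visits is not. A swab at a given visit reflects conversion since the previous swab; the form always reflects the last 7 days. When visits drift apart, outcome and covariate describe different periods.

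**Working it through.** **1. Coverage of the form, item by item**

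| Appendix III item | Subject | Setting |
|---|---|---|
| 1 | Shifts and hours | ICU, ED, COVID unit |
| 2 | Aerosol-generating procedures | Work |
| 3 | Extensive body contact | Patient |
| 4 | Prolonged close contact, counted over shifts | Patient |
| 5 | Adequacy of PPE | PPE |
| 6 | Other unprotected exposure, open | Patient example only |

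The demographics named in Section 9.8.4 are sex, age, race and ethnicity, so household contact is not picked up there either. This part of the point needs no arithmetic and does not depend on visit timing.

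**2. Interval between adjacent post-baseline visits**

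Inputs: planned spacing 7 days (Section 7.1), window ±3 days (Table 3), look-back 7 days (Section 9.8.12). The plan states no figure for coverage, so there is none to reproduce.

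Let a and b be the shifts of two adjacent visits from their planned days.

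- Interval = 7 + b − a. Minimum 7 − 3 − 3 = 1 day (Day 10 to Day 11). Maximum 7 + 3 + 3 = 13 days (Day 4 to Day 17).
- Days unasked = max(0, b − a), at most 6. Days covered twice = max(0, a − b), at most 6.
- Of the 7 × 7 = 49 permitted pairs, 7 give exactly 7 days, 21 leave a gap and 21 overlap.
- Mean gap = (1×6 + 2×5 + 3×4 + 4×3 + 5×2 + 6×1)/49 = 56/49 = 1.14 days, if all pairs are equally likely. Mean overlap is the same.

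Day 1 to Day 7 is different: the visit may fall on Day 4 to Day 10, so the interval is 3 to 9 days and the gap at most 2.

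**3. Share of follow-up unasked**

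The documents give no distribution of visit timing. Assume independent shifts, uniform over ±h days. Follow-up from Day 1 to a last visit averaging Day 49 is 48 days, made up of the Day 1 to Day 7 interval and six later intervals.

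| h | Mean gap, each later interval | Mean gap, Day 1 to Day 7 | Unasked days | Share of 48 |
|---|---|---|---|---|
| 0 | 0 | 0 | 0 | 0% |
| 1 | 4/9 = 0.444 | 0 | 6 × 0.444 = 2.67 | 5.6% |
| 2 | 20/25 = 0.800 | 1/5 = 0.200 | 4.80 + 0.20 = 5.00 | 10.4% |
| 3 | 56/49 = 1.143 | 3/7 = 0.429 | 6.86 + 0.43 = 7.29 | 15.2% |

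Days of follow-up covered twice, by the same route: 0%, 5.6% (2.67/48), 10.0% (4.80/48) and 14.3% (6.86/48).

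**4. Missed visits and screening**

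One missed visit between two attended post-baseline visits makes the interval 14 ± 6 = 8 to 20 days, leaving 1 to 13 days unasked (7 if the attended visits are on their planned days). Screening to Day 1 may be 0 to 30 days, leaving at most 30 − 7 = 23 days unasked, all before treatment.

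**The case against.** Several points on the other side stand.

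- A reader might infer that the form asks only about work and records no home exposure. The documents do not support that. Item 6 is open, its patient contact is only an example, and Section 9.8.12 does not limit exposure to work. A home contact could be volunteered; it is not prompted.
- A reader might infer that family contact is the main route of infection for these participants. The 85% is an upper figure from general records in China, not from health care workers or this site. The same section stresses close, unprotected exposure, which is what the form asks about.
- The 15% figure needs uniform scatter across the full window. Dosing and swabbing are also weekly, and visits exactly on schedule leave nothing unasked.
- A fixed 7-day recall is defensible as a weekly intensity with a constant denominator. Neither document sums exposure over visits, so overlap is not necessarily double counting. Switching every item to recall since the last visit would make the yes/no answers depend on interval length.
- The screening gap is weak: it is pre-treatment, and the form is repeated on Day 1 with a swab.
- Both arms follow the same schedule, so a timing error that differs by arm is not shown.

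One defence is only partial. SAP Section 7 provides for imputation when more than 5% of data are missing. That can address a missed visit, but a late visit yields a completed form, so its unasked days do not appear as missing. Nor does any of this answer the absence of a prompt for contact outside work.

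**Conclusion.** The point holds, chiefly on content. Household and community exposure is not prompted in a comparison of self-chosen arms whose adjusted analysis depends on measured confounders, and this is so even with perfect visit timing. The Introduction shows that such exposure is plausible, not how large it is here.

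The timing point is secondary. Post-baseline visits may be 1 to 13 days apart, with a plan of 7. The share of follow-up unasked runs from 0% to about 15% as the assumed scatter goes from ±0 to ±3 days, and is higher after a missed visit.

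Two stronger conclusions might be drawn and should not be. One is that the form is the plan's designated adjustment variable: neither document names it, or any other covariate, for the model. The other is that the treatment comparison is shown to be biased: residual confounding is possible in either direction, but its size and direction cannot be computed from the documents.

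**What to change.** 1. Add one dated yes/no item to Appendix III on close contact outside work, including the household, with a person with confirmed or suspected COVID-19.
2. In SAP Section 6.1, name this item and the work-exposure measure as covariates in the adjusted model.
3. Record on the form the date of the last completed visit. When the interval exceeds 7 days, also ask shifts and hours since that date, and analyse them per day covered.
4. Keep the 7-day period for the existing yes/no items and print it on the form, or ask for dates, so that a positive answer does not become likelier merely because the interval was longer. Amend Section 9.8.12 to match.

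The cost is one more question, slightly longer recall after late or missed visits, and the added model terms. Under the Synopsis, the registry follows the same assessments apart from blood testing, so one revised form serves both groups.

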9.8.13. Pregnancy Test

WOCBP (see [Section 9.6](#)) will self-report on their pregnancy status. Any subject who becomes pregnant during the study must discontinue taking study drug immediately. See [Section 9.6.3](#) for a description of procedures to be followed in case of pregnancy.

9.8.14. Study Drug Administration

Subjects should self-administer two capsules on day 1 following by two capsules once a week after that (preferably in the morning) until the end of the study. A bottle of tablets will be included in each subject's study drug kit.

A vomited dose must not be replaced. A double dose (*e.g.*, missed dose from previous week and dose for current week) must not be taken.

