6.1.1. Primary Objective

To assess the efficacy of hydroxychloroquine 400 mg twice a day (two 200 mg tablets twice a day) on day 1 followed by two 200 mg tablets once a week for a total of 7 weeks in the prevention of COVID-19 infection

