9.4. Treatment Compliance

The investigator or his/her designated and qualified representatives will only dispense study drug to subjects enrolled in the study in accordance with the protocol. The study drug must not be used for reasons other than that described in the protocol. Subjects who miss more than 25% of the total number of expected doses will not be considered treatment-compliant.

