10. STUDY DRUG MATERIALS AND MANAGEMENT

10.1. Study Drug

Hydroxychloroquine tablets will be used in this study.

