10.4. Study Drug Administration

Please refer to [Section 9.8.14](#) for details on study drug administration. Clear instructions will be provided to the subject regarding the number and type of capsules to be ingested at each study drug administration time point listed in [Table 3](#). Subjects must be instructed to continue taking study drug twice on day 1 (two 200 mg twice a day) and once weekly (two 200 mg) after that for a total of 7 weeks unless: (1) subject has been otherwise instructed by the investigator or (2) the subject has been formally discontinued from the study.

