10.5. Study Drug Accountability

The investigator, or designee, will maintain a record of all study drug received, dispensed, and returned to the Sponsors' designee. No study drug shall be destroyed by the clinical site unless directed in writing to do so by the Sponsor's quality assurance department. Study drug bottles and any unused capsules should be returned to the study staff for eventual disposition by the Sponsor. The number of capsules returned at each visit will be recorded for each bottle in the kit.

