This prospective open label trial will study the safety, tolerability, and efficacy of hydroxychloroquine in qualified health care workers. Qualified individuals will be administered hydroxychloroquine twice a day on day 1 (two 200 mg twice a day) and once a week (two 200 mg) afterwards for a total of 7 weeks. Dose de-escalation is permitted during the study if indicated clinically. All study individuals will follow the same visit and assessment schedule. Following study enrollment, participants will be scheduled to be assessed in person at Days 7, 14, 21, 28, 35, 42 and 49.

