5.2. Per Protocol (PP)

All randomised study subjects completing the whole study period (complete cases)

6. Analyses

All statistical analyses and data summaries will be performed using SAS® (Version 9.1 or higher) or other validated software. The SAP will serve as the final arbiter of all statistical analyses. Data will be summarized overall using descriptive statistics. Continuous data will be summarized with number of subjects (n), mean, median, minimum, maximum, relevant quartiles, standard deviation, coefficient of variation, and geometric mean (where applicable). Categorical data will be summarized using frequency counts and percentages. Chi Square or Fisher exact test will be used for comparing binary outcomes between treatment and control groups. Continuous variables will be compared between the study groups by means of two sample T test or Wilcoxon-rank-sum test.

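### Protocol 9.8.14 tells subjects to take 400 mg on Day 1, half the 800 mg dose in the primary objective, Protocol 7.1 and 10.4, and the SAP

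*Protocol*

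**What the plan says.** The primary objective in Protocol 6.1.1 names the regimen under test as "hydroxychloroquine 400 mg twice a day (two 200 mg tablets twice a day) on day 1". After that the dose is 400 mg weekly, and the whole course lasts 7 weeks. The synopsis, Protocol 7.1, and SAP sections 2 and 3.2 state the same Day 1 dose.

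Protocol 9.8.14 instead says: "Subjects should self-administer two capsules on day 1 following by two capsules once a week after that". It gives no second intake on Day 1 and no strength per unit.

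Protocol 10.4 refers the reader to 9.8.14 for administration details. In the same paragraph it states the larger dose: "Subjects must be instructed to continue taking study drug twice on day 1 (two 200 mg twice a day) and once weekly".

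The dosage form also varies. Protocol 10.1 says: "Hydroxychloroquine tablets will be used in this study". Sections 9.8.14, 10.4 and 10.5 speak of capsules, although the sentence after the dosing instruction in 9.8.14 refers to a bottle of tablets.

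On compliance, Protocol 9.4 says: "Subjects who miss more than 25% of the total number of expected doses will not be considered treatment-compliant". It does not say how many doses are expected, or whether a dose is an intake, a tablet or a dosing day.

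**The concern.** Subjects dose themselves, and 9.8.14 is the procedure from which a participant instruction would naturally be drafted. It gives Day 1 the same count as a weekly dose, so the larger first-day dose disappears. A subject instructed from it would not receive the regimen named in the primary objective. The shortfall would not be recovered later either, because the same section forbids adding a missed dose to the next week's dose.

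The protocol treats a halved dose as a clinical decision. Section 7.3.1 allows it when clinically indicated, with the reasons to be discussed with the medical monitor beforehand. Following 9.8.14 would halve Day 1 with neither step. While 9.8.14 and 10.4 disagree, it is also unclear which Day 1 intake is the protocol deviation to be documented under 15.6.

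The stakes are limited to the dose delivered in the treated arm and to how compliance is reported.

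**Working it through.** **Inputs**

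- Strength: 200 mg per tablet (synopsis, name of investigational product). Section 9.8.14 states no strength, so 200 mg is assumed for its capsules. No other strength appears in the documents.
- Intended Day 1 dose: two tablets, twice (synopsis; Protocol 6.1.1, 7.1, 10.4; SAP 2, 3.2).
- Day 1 dose in 9.8.14: two units, with no repeat stated.
- Weekly dose: two tablets, the same in every statement.
- Dosing visits: Table 3 marks drug administration on Days 1, 7, 14, 21, 28, 35 and 42, which is Day 1 plus six weekly doses.

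**Day 1 dose** = units per intake × intakes × 200 mg

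- Intended: 2 × 2 × 200 = 800 mg, which reproduces the 400 mg twice a day of the primary objective.
- 9.8.14 as written: 2 × 1 × 200 = 400 mg.
- Ratio: 400 / 800 = 0.50.

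**Whole course per Table 3**

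| | Tablets | Dose |
|---|---|---|
| Intended | 4 + 6 × 2 = 16 | 3,200 mg |
| 9.8.14 as written | 2 + 6 × 2 = 14 | 2,800 mg |
| Shortfall | 2 | 400 mg = 12.5% |

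Section 9.8.14 says dosing runs to the end of the study, and Table 3 labels Day 49 the end-of-study visit. If a Day 49 dose were given, the totals would be 3,600 mg and 3,200 mg, a shortfall of 400 / 3,600 = 11.1%. Table 3 marks no administration on Day 49, so 12.5% is the figure to use. The Day 1 ratio is the same either way.

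**Compliance under 9.4**, taking an expected dose to be an intake (an assumption)

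- Expected intakes: 2 + 6 = 8. Intakes under 9.8.14: 1 + 6 = 7.
- Subject who follows 9.8.14 fully: 1/8 = 12.5% missed, classed as compliant.
- Same subject who also misses one weekly dose: 2/8 = 25.0%, still compliant because the rule requires more than 25%.
- Counting tablets gives the same values: 2/16 = 12.5% and 4/16 = 25.0%.
- If the seven intakes of 9.8.14 were the denominator, the class would change only at exactly two missed intakes: 2/7 = 28.6% against 2/8 = 25.0%.

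**Does compliance reach an analysis?** No. SAP 6.1 and Protocol 12.2.1 define the primary efficacy population by receipt of at least one dose. SAP 5.1 uses receipt of drug and a post-baseline assessment, and SAP 5.2 uses completion of the study period. The power calculation does not use the dose.

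**The case against.** The best case on the other side is that this is a drafting slip which the documents already resolve. The 800 mg dose is stated repeatedly in the protocol and SAP. Section 10.4 says what subjects must be told, while 9.8.14 says only what they should do, and the synopsis says the drug will be prescribed at the twice-daily Day 1 dose. The phrase in 9.8.14 could also have been meant as the amount per intake. No participant instruction or label carrying the 9.8.14 wording is among the documents.

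A second point is that drug accountability might expose the shortfall. Protocol 10.5 says: "The number of capsules returned at each visit will be recorded for each bottle in the kit". Drug is collected from Day 7 onward, so two leftover tablets would show if the intended supply had been dispensed.

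Much of this stands. The intent is clear, and under-dosing is a risk, not an established fact. The compliance arithmetic rests on an undefined term and feeds no stated analysis. The per-intake reading is weaker: the sentence does not say so, and it uses the same count for the once-weekly dose. The accountability check works only if the larger supply was dispensed, and even then the 9.4 rule would still class the subject as compliant. Clear intent makes the correction certain. It does not make a contradictory dosing instruction harmless when 10.4 itself points to it.

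**Conclusion.** The concern holds. Section 9.8.14 is wrong as written: it gives 400 mg on Day 1 where the primary objective and every other full statement of the regimen give 800 mg. That is 50% less on Day 1 and 12.5% less over the course in Table 3. The dose figures assume 200 mg units, and the course figure assumes Day 42 is the last dose. The compliance figures also assume that expected doses are counted as intakes or tablets.

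This is an internal inconsistency that should be fixed, not a flaw in the design or the analysis. It bears on the dose delivered and on compliance reporting. The documents give no basis for estimating how a halved Day 1 dose would alter infection risk.

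**What to change.** Amend Protocol 9.8.14 to say: two 200 mg tablets twice on Day 1, then two 200 mg tablets once a week, with the last dose on Day 42 as in Table 3. Replace capsules with tablets in 9.8.14, 10.4 and 10.5. Check the participant instructions and kit labels against the corrected text. If dosing has already taken place, use the same check, together with the returned-tablet counts, to establish which Day 1 dose subjects were told to take.

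Optionally, add to 9.4 that eight intakes (16 tablets) are expected, for compliance reporting only.

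The cost is one line of protocol wording, the matching change of terms and a document check. No new data, subjects or analyses are needed.
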